# **Version History**

Version #	Version Date	Significant Changes from Previous Version
Version 1	18-Feb-2022	Original Protocol Version

**Table 1: Abbreviations** 

ADE	Adverse device effect
AE	Adverse event
BCVA	Best Corrected Visual Acuity
CFR	Code of federal regulations
CRF	Case report form
ECP	Eye Care Professional
EDC	Electronic data capture
FDA	Food and Drug Administration
GCP	Good Clinical Practice
ICH	International Conference on Harmonization
IDE	Investigational Device Exemption
IRB	Institutional Review Board
IWRS	Interactive web response system
LAR	Legally Authorized Representative
MRSE	Manifest Refractive Spherical Equivalent
PHI	Protected health information
SAP	Statistical analysis plan
SAE	Serious adverse event
SCA	Sphere, Cylinder, Axis
SOC	Standard of care
UADE	Unanticipated adverse device effect
VA	Visual acuity

Table 2 Definitions of conditions and materials

Astigmatism	a refractive problem with the eye related to the shape of the lens, which causes blurry vision
Hyperopia	farsightedness
Myopia	nearsightedness
Presbyopia	a condition related to aging that causes lens of the eye to have trouble focusing
Phoropter	Device to perform traditional refraction eye examination

# STUDY SYNOPSIS

An evaluation of the LFR-260 against a traditional phoropter in visual acuity testing LFR-260-101	
LFR-260-101	
2x2 Crossover	
2 sites, 3 locations	
Up to 108 subjects (216 eyes)	
Healthy volunteers	
ntional Device LFR-260 in a standard visual acuity test	
Any 510(k) exempt phoropter legally marketed in the US	
(Refractor, Manual, Non-Powered, Including Phoropter)	
To evaluate the agreement of LFR-260 (investigational device) to	
traditional phoropter (comparator device) when applied in visual	
acuity test in subjects undergoing a full routine eye examination.	
The primary effectiveness endpoint is to demonstrate that the	
LFR-260 is within 0.5D (+/-) in measuring sphere and cylinder	
results and within 10 degrees for axis results among subjects with	
low astigmatism and within 5 degrees among subjects with moderate	
to high astigmatism from the traditional phoropter in a very large	
proportion of subjects.	
2 U H H H H H H	

[figure not shown]
# Statistical Considerations

The objective of the statistical analysis is to evaluate agreement in sphere, cylinder, and axis measurements between LFR-260 and traditional refraction performed by a traditional phoropter. Specifically, the subjective manifest refraction measured by means of a traditional phoropter will serve as the reference control and is considered to be the gold standard for the purpose of this evaluation.

The accuracy of the acuity measurement obtained by the LFR-260 will be evaluated for both cases (uncorrected, corrected) measured with the conventional phoropter. It will be assessed comparing the LFR-260 acuity measurement to the conventional acuity measurement using a Snellen chart (scored to the letter), with similar analyses used for the refractive components.

For each measurement, the paired difference will be computed. Good clinical agreement is defined a priori as  $\leq \pm 0.5$  D for sphere and cylinder measurements and  $\leq \pm 10$  degrees for axis measurements for subjects with low astigmatism and  $\leq \pm 5$  degrees for axis measurements for subjects with low astigmatism.

The unit of analysis will be the individual eye. Overall device performance will be summarized as the number of and percentage of eyes meeting three of the good clinical agreement criteria listed above.

the mean of measurements will characterized.

A supporting analysis will evaluate the vector difference between investigational device measurements and the gold standard in terms of sphere and cylinder measurements. The vector differences is square root of (X1-Y1) + (X2-Y2) where the X1 and X2 are measurements of sphere and cylinder using the investigational devices and Y1 and Y2 are the same measurements using the gold standard.

Homogeneity of treatment effects across sites will be evaluated comparing site level differences between the investigational device and the gold standard separately for sphere, cylinder, and axis and also for the vector analysis of sphere and cylinder.

Similarly, differences between measurements from the investigational device and the gold standard device will be summarized by gender, age category, race, and ethnicity to investigate consistency or heterogeneity of the treatment effect across those subgroups, separately for sphere, cylinder, and axis and also for the vector analysis of sphere and cylinder.

The primary analysis will be based on the intent-to-treat (ITT) analysis set and will use multiple imputation to address missing values. The multiple imputation (MI) model will include sphere, cylinder, and axis measurements for both the investigational device and the gold standard device and baseline characteristics including age and gender. Analyses will be repeated in a per protocol analysis set that includes eyes with complete data.

Reliability (repeatability and reproducibility) of LFR-260 will be conducted in a subset of subjects for which measurements will be obtained twice in an office context. This analysis will be repeated in a remote context. Reliability will be evaluated using intraclass correlations for each of the continuous measurements, sphere, cylinder, and axis.

.

# Study Criteria

# **Inclusion Criteria**

Participants must fulfill all of the following criteria in order to be eligible for the study:

- 1. The participant or legal guardian is willing and able to understand, sign and date the Ethics committee approved study specific Informed Consent Form.
- 2. The participant is a male or female between the ages of 12 and 65 (inclusive).
- 3. The participant has a history of the following:
  - No more than mild to moderate far-sightedness or near-sightedness (i.e. Spherical equivalent refraction (SER) between +10 to -15).
  - o an astigmatism of 2.5D or less.
  - o an anisometropia of 1.5D or less.
- 4. The participant is free of ocular and systemic abnormalities that might affect visual functions.

#### **Exclusion Criteria**

Participants will be excluded from participation in the study if any of the following criteria are met at screening:

- 1. The participant has diabetes mellitus (Type 1 or 2).
- 2. The participant has an autoimmune condition.
- 3. The participant is pregnant (self-reported).
- 4. The participant has an active corneal or conjunctival infection.
- 5. The participant has an active corneal, conjunctival, or intraocular inflammation (i.e. uveitis).
- 6. The participant has diabetic retinopathy.
- 7. The participant has glaucoma or ocular hypertension.
- 8. The participant has macular degeneration.
- 9. The participant has had a previous ocular surgery.
- 10. The participant has ocular and systemic diseases or abnormalities that might affect visual functions.
- 11. The participant has a history of amblyopia, strabismus, or any other binocular vision abnormality.
- 12. The participant has a history of AMD (age macular degeneration).

- 13. The participant is a prisoner, a transient or has been treated for alcohol and/or drug abuse in an inpatient substance abuse program within 6 months prior to proposed study enrolment.
- 14. The participant will not be able to complete questionnaires.
- 15. The participant is currently in an investigational study for a similar purpose.
- 16. The participant, in the judgment of the Investigator, may be inappropriate for the intended study procedures.

Evolution Optiks, Ltd.

#### 1.0 Introduction

# 1.1 Background and Significance

The LFR-260 was designed by comparing its capabilities against an optical bench and physical lenses. Further, it has been tested for quality of image composition and correctness at all the points on the spectrum of settings that we intend to cover.

# 1.2 Device Name and Intended Use

The LFR-260 is intended to be used for distance vision testing in any environment, may it be in optometric clinics or in the field outside of the clinic, because of its compact form factor and portability.

The LFR-260 is an application-controlled instrument providing capabilities for distance vision testing including sphere, cylinder, and axis. The visual acuity and eye subjective manifest refraction determination will always be administered by an eye care professional (ECP) licensed and registered by the appropriated body in the region intended to be used. The instrument is designed in a way that it will only work with approved personnel and the use of secure credentials.

The device is intended to be used in patients aged from 12-65 years old with healthy visual systems and a refractive error no bigger than (+10 to -15D) and astigmatism no bigger than 2.5D (if any).

# 1.3 Regulatory Status and Clinical Data

The LFR-260 has not been cleared for use outside of this investigation.

# 2.0 Objectives and Study Endpoints

# 2.1 Objective

The aim of this trial is to establish if LFR-260 (investigational device) is **in agreement with a gold standard** in effectiveness to a traditional phoropter (control device) when applied in visual acuity test in subjects undergoing a full routine eye examination. This will be demonstrated by measuring that the LFR-260 is within 0.5D (+/-) in sphere and cylinder results and within 10 degrees for axis results from the traditional phoropter measurements.

#### 2.2 Rationale

The purpose of this test is to evaluate the agreement to a gold standard of the refraction results provided by LFR-260 compared to a traditional refraction assessment conducted using a traditional phoropter (commonly used at optometry offices as the standard device used for measuring refraction).

Refraction test is part of a routine eye examination and from now on we will use the terms refraction test and vision test indistinctly. We propose the use of LFR-260 to provide information of the visual capabilities of the patient. The test will be provided and supervised by a qualified ECP appropriately registered and licensed in the region where the test.

# 2.3 Primary Endpoints

The primary effectiveness endpoint is to demonstrate that the LFR-260 is within 0.5D (+/-) in measuring sphere and cylinder results and within 10 degrees for axis results from the traditional phoropter. Precision testing will also be conducted to confirm repeatability and reproducibility of the LFR-260.

#### 2.4 Secondary outcomes

# 2.4.1 Secondary Endpoints

- Patient satisfaction with LFR-260 device Quad view
- Eyecare provider satisfaction with LFR-260 related to usability, convenience

# 2.5 Hypotheses

# 2.5.1 Primary Effectiveness Hypothesis

The primary hypothesis for this study is that the probability of simultaneously achieving good clinical agreement for sphere, cylinder, and axis exceeds a performance goal (PG) for measurements made by the LFR-260 compared to those obtained using traditional phoropter. The *a priori* PG is 0.80. Good clinical agreement is defined as a sphere and cylinder measurements that are within +/- 0.5 D and within 10 degrees for axis among subjects with low astigmatism and within 5 degrees among subjects with moderate to high astigmatism.

# 3.0 Subject Selection

# 3.1 Number of Sites / Investigators

Investigators responsible for the conduct of this study in compliance with this protocol will be qualified ECPs (licensed optometrist or ophthalmologist) who are skilled in refraction testing via a traditional phoropter. Two (2) sites at 3 locations (one site has multiple satellite locations) in the United States will be selected for participation in this study. Each location will have 2 ECPs available for testing/evaluation for a total of 6 different ECPs for the study.

# 3.2 Number of Subjects

Accounting for lost to follow-up, a total of up to 108 subjects (216 eyes) will be enrolled in the study. To control any effect of the instrument induced myopia, we expect to enroll an age tiered distribution of participants of the following approximate percentages:

- Approximately 45% Pediatrics (age from 12 until ≤21 years)
- Approximately 55% Adults/Geriatrics (age between 22-65)

A large portion of the subjects belongs to pediatric population such distribution will address the presence or absence of induced instrument myopia.

# 3.3 Study Arms

All subjects will be randomized by treatment order to the following refractor testing methods:

- Group I: LFR-260
- Group II: Traditional Phoropter

#### 3.4 Inclusion criteria

Participants must fulfill all of the following criteria in order to be eligible for the study:

- 1. The participant or legal guardian is willing and able to understand, sign and date the Ethics committee approved study specific Informed Consent Form.
- 2. The participant is a male or female between the ages of 12 and 65 (inclusive).
- 3. The participant has a history of the following:
  - O No more than mild to moderate far-sightedness or near-sightedness (i.e. Spherical equivalent refraction (SER) between +10 to -15).
  - o an astigmatism of 2.5D or less.
  - o an anisometropia of 1.5D or less.
- 4. The participant is free of ocular and systemic abnormalities that might affect visual functions.

#### 3.5 Exclusion criteria

Participants will be excluded from participation in the study if any of the following criteria are met at screening:

- 1. The participant has diabetes mellitus (Type 1 or 2).
- 2. The participant has an autoimmune condition.
- 3. The participant is pregnant (self-reported).
- 4. The participant has an active corneal or conjunctival infection.
- 5. The participant has an active corneal, conjunctival, or intraocular inflammation (i.e. uveitis).
- 6. The participant has diabetic retinopathy.
- 7. The participant has glaucoma or ocular hypertension.
- 8. The participant has macular degeneration.
- 9. The participant has had a previous ocular surgery.
- 10. The participant has ocular and systemic diseases or abnormalities that might affect visual functions.
- 11. The participant has a history of amblyopia, strabismus, or any other binocular vision abnormality.
- 12. The participant has a history of AMD (age macular degeneration).
- 13. The participant is a prisoner, a transient or has been treated for alcohol and/or drug abuse in an inpatient substance abuse program within 6 months prior to proposed study enrolment.
- 14. The participant will not be able to complete questionnaires.
- 15. The participant is currently in an investigational study for a similar purpose.
- 16. The participant, in the judgment of the Investigator, may be inappropriate for the intended study procedures.

# 4.0 Study Overview

# 4.1 Study Design

This study is organized as multicenter, randomized cross-over study trial. There are two groups involved in the trial, the investigational group and the active control group. The comparison with a placebo group is not part of the trial for ethical reasons.

# 4.2 Investigational group

The LFR-260 is a portable digital refractor which allows for determination of refractive error as well as for fully remote refractions while social distancing. The device offers a solution that embodies all the aspects that are typically associated with a refraction evaluation in a mobile approach while giving the practitioner full control, ease of use and patient comfort.

Figure 1: Image of the LFR-260

A standard phoropter on the market is comprised of a set of lenses which can be adjusted by an ECP to guide a patient through different settings as in "do you see better now?" format. In contrast, the objective device, LFR-260, achieves the same functionality but relies on a digital approach based on a micro lens array, a high-density embedded display, and a tunable lens. The device was developed taking a different approach that allows a significant reduction in the number of lenses, allowing higher portability and smaller footprint. The lower number of lenses does not compromise functionality compared to other traditional solutions. With these components, the LFR-260 provides the same capabilities as traditional lens systems, however in a portable, lightweight format.

The instrument will be able to perform traditional refractive tests with the standard optotypes (Snellen, ETDRS, Landolt C, LEA symbols) such as:

• Determining the required spherical correction

• Determining the required astigmatic correction measuring with JCC (Jackson cross-cylinder) – magnitude and direction.

# 4.3 Control group

The control group is a traditional refraction performed by a phoropter. The results for both refractions will be recorded separating the components Sphere (S), Cylinder (C) and Axis (A). A calculation of the spherical equivalent will be performed at the end of the visit and both values will be recorded in the study documentation. The best corrected visual acuity for each measurement will be recorded.

# 4.4 Visual Acuity Testing Procedure

All the subjects will undergo the standard visual acuity testing using both the LFR-260 and the traditional phoropter. Both eyes will be tested, always starting with the right eye. Both eyes will be tested with a traditional phoropter and the LFR-260. The subject will be seated on a height adjustable chair to ensure comfort during the test. Once the subject is seating comfortably the examiner will measure the distance between the outer canthus of the eye and the visual acuity to be used. The left eye will be patched while testing the right eye and vice versa. They could be covered with the occlude or using the masking capabilities of the LFR-260.

The following outcomes will be measured (for both eyes):

- Unaided VA
- Aided VA
- Distance for the test

Evaluation of the refractive state should be performed by reading the Snellen chart (or equivalent depending on the patient) at 20 feet (or adjusted to the appropriate distance depending on the dimensions of the actual optometric office). The subject should be informed that the chart only includes letters (or equivalent for patient population).

Outcomes will be recorded. If a line was incomplete, the scored letters should be added to the VA. The goal is to obtain best corrected visual acuity (20/20 Snellen) to ensure that the highest level of visual acuity possible for the patient.

Visual acuity testing will be performed without the use of cycloplegic agents and or pupil dilation at all times. To control the potential effect of instrument myopia we will propose starting the examination using the fogging method to relax any potential accommodation.

# 4.5 Test sequence

In the traditional refractor procedure of Snellen charts (or equivalent), if the patient cannot see a letter, the practitioner moves the patient closer to the chart 1m at the time. In the case of LFR-260, the letter sizes will adjust to simulate such movement and change of perceived size and recorded accordingly. Such adjustment should take place until the subject can see the top letters. The smallest letter the subject can see clearly would be considered the VA for distance.

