# Actual test sequence:

- a) Screening phase: In which the examiner will initially determine by single letter presentations what would be the smallest Snellen chart (or equivalent) level at which the subject will correctly identify letters.
- b) Testing phase: the examiner will start presenting letters of the size determined at the screening phase and smaller ones.
- c) Test continuation: if a letter is missed at a level, one level larger will be added to the testing. If a letter is correct at a level, one level smaller will be added to the mix.
- d) Acuity determination: Tests of 5 letters at each level until smallest level with 5/5 letters correct and the smallest level with 0/5 correct are determined.
- e) Quad view: at any time during a refraction, the ECP may provide a patient with a "quad view". This mode shows four different prescriptions simultaneously and allows the patient to switch from a memory-based decision to a solely vision-based decision.

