#### 4.6 Letter scores calculation

With the lens correction obtained and present either on the phoropter or the LFR-260, the subject will be asked to read the Snellen chart (or equivalent) emphasizing that each letter will be scored and will ask the subject to take their time in answering in order to achieve best identification. The examiner will record each letter identified correctly on a score sheet. If a letter is not correctly recognized it will not be recorded, each correct letter is a point. The score of each line, even if zero, and the total score for the eye will be recorded right after the examination and recorded in the patient chart and the case report form.

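### The supporting acuity comparison can be biased, because control subjects approach the chart while the LFR-260 only enlarges letters, and section 4.5 scores acuity differently from section 4.4 and the synopsis

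*Combined protocol and SAP*

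**What the plan says.** The synopsis (Statistical Considerations) plans to assess LFR-260 acuity, uncorrected and corrected, by "comparing the LFR-260 acuity measurement to the conventional acuity measurement using a Snellen chart (scored to the letter"), with analyses like those for the refractive components, that is, paired differences. Section 7 does not carry this analysis forward. The documents give no margin, SD or sample size for acuity. Acuity agreement is not a listed secondary endpoint (2.4.1), and the primary endpoint uses sphere, cylinder and axis only (7.3, 7.4).

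The definition of acuity is therefore left to sections 4.4 to 4.6:

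- **4.4** starts with "reading the Snellen chart (or equivalent depending on the patient) at 20 feet", adjustable to the office. It lists the test distance among the recorded outcomes and adds letters read on a partial line to the VA.
- **4.5, control:** if a letter is not seen, "the practitioner moves the patient closer to the chart 1m at the time".
- **4.5, LFR-260:** "In the case of LFR-260, the letter sizes will adjust to simulate such movement and change of perceived size".
- **4.5, end of the step:** "Such adjustment should take place until the subject can see the top letters".
- **4.5, score:** "The smallest letter the subject can see clearly would be considered the VA for distance".
- **4.6**, with the lens correction in place, counts letters: "each correct letter is a point".

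**The concern.** The two devices respond differently when an eye cannot read the top letters. Walking toward a real chart makes the letters subtend a larger angle and also brings the target optically nearer. Enlarging letters reproduces the first effect but not the second. For an uncorrected myope, a nearer target means less blur, so the same eye could be tested with less defocus on the control than on the LFR-260. Part of the paired difference in uncorrected acuity would then come from the procedure and not from the device.

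Two related gaps concern the score. A letter read at a shorter distance represents worse acuity than the same letter read at 20 ft, and the plan does not say that control acuity will be converted for distance. In addition, the smallest-letter rule in 4.5 does not agree with 4.4 or the synopsis, so the same responses can be recorded as different acuities.

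**Working it through.** **The plan's own figure.** The only stated power is for the primary endpoint (7.5): 216 eyes, true probability 0.90, goal 0.80, one-sided exact binomial at 0.05. Treating eyes as independent, as the plan does, the smallest passing count is 183 eyes. The exact alpha is 0.0461 and power is 99.5%, which matches the stated 99%. Acuity does not enter this calculation.

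**Inputs.** The starting distance is 20 ft = 20 × 0.3048 = 6.096 m (4.4), and steps are 1 m (4.5). Three assumptions are not in the documents: the LFR-260 holds vergence fixed, the eye does not accommodate, and the minimum angle of resolution of a blurred eye is proportional to its residual defocus.

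**Formulas, with d the distance after k steps (6.096 − k):**

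- Vergence change = 1/d − 1/6.096. At five steps: 1/1.096 − 1/6.096 = 0.912 − 0.164 = 0.748 D.
- Acuity gain from reduced blur in a myope of M dioptres = log10[(M − 0.164)/(M − 1/d)]. For M = 3 at three steps: log10(2.836/2.677) = 0.025.
- Error if distance is not converted = log10(6.096/d). At one step: log10(6.096/5.096) = 0.078.

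| Steps | d (m) | Vergence change (D) | Blur gain, -1 D | -2 D | -3 D | -6 D | Unconverted distance |
|---|---|---|---|---|---|---|---|
| 1 | 5.096 | 0.03 | 0.017 | 0.008 | 0.005 | 0.002 | 0.078 |
| 2 | 4.096 | 0.08 | 0.044 | 0.019 | 0.012 | 0.006 | 0.173 |
| 3 | 3.096 | 0.16 | 0.092 | 0.039 | 0.025 | 0.012 | 0.294 |
| 4 | 2.096 | 0.31 | 0.204 | 0.081 | 0.051 | 0.024 | 0.464 |
| 5 | 1.096 | 0.75 | 0.980 | 0.227 | 0.133 | 0.060 | 0.745 |

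The last five columns are in logMAR. Except for the -1 D eye at five steps, every blur gain shown is smaller than the unconverted-distance error in its row.

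For an unaccommodated hyperope of H dioptres, approach adds blur: log10[(H + 1/d)/(H + 0.164)]. At +2 D this runs from 0.006 (one step) to 0.129 (five steps), against the control. Testing is without cycloplegia (4.4), so a hyperope who accommodates would show less of this.

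The unconverted-distance error makes the control look too good. It enters the paired difference when LFR-260 acuity is recorded at its enlarged letter size but control acuity is read off the chart as if at 20 ft. If neither is converted and both need the same number of steps, it cancels in the difference, although both acuities are then wrong.

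**Scoring.** Take an uncorrected eye with five of five letters at 20/20 and two of five at 20/15. The smallest-letter rule in 4.5 gives 20/15 if the two letters count as seen clearly, which is log10(15/20) = -0.125 logMAR. The partial-line rule in 4.4 gives 20/20 plus two letters. With linear credit per letter, that is 2/5 × -0.125 = -0.050. The same responses differ by 0.075 logMAR according to the section followed.

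**The case against.** The strongest reply is that the bias rests on an unstated property of the device. Section 4.5 mentions only letter size, but 4.2 lists a tunable lens among the components, and the documents do not say whether it moves during this step. That stands: the bias is possible, not shown. It also stands that the step selects very blurred eyes, in which a fraction of a dioptre matters least. The low myopes with the largest tabulated effects are the least likely to miss the top letters. Test distance is recorded, so the angular error is correctable, though nothing says it will be corrected.

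A reader might go further in ways the documents do not support:

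- **That the -15 D entry limit makes matters worse.** The effect is smallest there: at most 0.022 logMAR at five steps, under the same assumptions.
- **That approach inflates the letter count in 4.6.** That count is taken with the correction in place. Eligibility excludes amblyopia and abnormalities affecting visual function, so a corrected eye that misses the top letters should be rare.
- **That the stopping rule "until smallest level with 5/5 letters correct and the smallest level with 0/5 correct are determined" sets the wrong bound.** Under step (c) of the test sequence a smaller level is added only after a correct letter. Descent therefore ordinarily ends at the first level with none correct, where smallest and largest coincide.
- **That the scoring conflict is itself a device bias.** No scoring rule is tied to a device. Apart from the smallest-letter sentence, the rules are letter-based and largely compatible.

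**Conclusion.** The supporting acuity comparison can be biased and is inconsistently scored. If the LFR-260 holds vergence fixed, approach favours the control in uncorrected myopes. The size is 0.025 logMAR or less through three steps at -3 D or worse, and up to 0.133 at five steps. It is larger in low myopes and reversed in unaccommodated hyperopes. These figures rest on the optical assumptions above, not on values in the documents. The larger exposure is distance: 0.08 to 0.75 logMAR over one to five steps if control acuity is not converted. The smallest-letter rule adds noise and analyst choice.

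A reader might infer that the trial's main conclusion is at risk. It is not: the primary endpoint contains no acuity measure, and its stated power does not change. This is a moderate defect in how a supporting outcome is defined, worth correcting before enrolment.

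**What to change.** 1. Delete the smallest-letter sentence in 4.5.
2. Define one letter-based score for both devices, converted to logMAR with the recorded test distance on the control and the simulated distance on the LFR-260. State it once and align the synopsis and 4.4 to 4.6 with it.
3. Choose one way to handle eyes that cannot read the top letters. Either keep the control chart at a fixed distance and use larger optotypes, recording an eye as below chart range when these run out; or base the uncorrected comparison on eyes that needed neither approach nor enlargement, and report the other eyes separately.

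The cost is protocol and case report form wording, with no added subjects or visits. The downside is that some very blurred eyes leave the uncorrected comparison, so it says less about them.
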